7.3 Baseline data

The following baseline data will be recorded from routine care forms:

- Demographic (age and sex) and anthropometric data (height and weight [body mass index and body surface area using the Du Bois formula will be derived]). Ethnic origin is collected because it affects glomerular filtration rate, which could modify the pharmacokinetics of TXA, as it is eliminated 100% by the kidneys. Information on these parameters can be collected at baseline if available or at follow up.
- Information about the injury, time of injury and time of IV TXA administration.
- Vital signs including blood pressure, temperature, heart rate, and respiratory rate.

- Standard clinical tests made on admission will be used to assess shock (base excess, lactate, and renal function).
- Treatments (intravenous fluids and blood products).

These parameters will be used to build a pharmacokinetic model that describes the TXA concentration in the blood over time following the TXA IM injection.

7.4 TXA IM administration and timing of biological samples

Eligible patients would have received 1 gram of TXA as an IV injection.²⁸ The time of the TXA IV injection is T_{-3} . Blood will be taken about ten minutes later (T_{-2})* and also immediately before the intramuscular TXA injection (T_{-1}). Post injection samples will be taken as per the schedule below. We understand that the care of the patient takes priority over the sampling schema and that sample times will inevitably differ from those indicated. If it is not possible to obtain a sample at the scheduled time, the sample should be collected as soon as feasible with the exact time of collection recorded. The main requirement is that two samples are taken before TXA IM injection and six after - with exact time recorded. Reasons for any delay will be recorded.

Pharmacokinetics: Blood samples (2 mL of venous blood in dry tube without anti-coagulant) will be taken at the following times, except T_{-3} and T_0 :

T_{-3} = TXA IV injection

T_{-2} = $T_{-3} + 10$ (± 5 min) if the clinical situation allows*

T_{-1} = immediately before IM injection

T_0 = TXA IM injection (minimum 1h 30 min after IV injection)

T_1 = $T_0 + 15$ min (± 15 min)**

T_2 = $T_0 + 45$ min (± 15 min)**

T_3 = $T_0 + 1$ h 30 min (± 30 min)**

T_4 = $T_0 + 3$ h (± 1 h)**

T_5 = $T_0 + 6$ h (± 1 h)**

T_6 = $T_0 + 10$ h (± 1 h)**

* If the clinical situation does not allow the collection of a blood sample within the time interval specified for T_{-2} , that sample should be taken as soon as possible up to 15 minutes before the IM TXA administration and the exact time of collection should be recorded on the patient's CRF.

** Because the main requirement is that every patient has six timed samples after the IM administration of TXA, if (in exceptional circumstances) a sample cannot be taken at the optimal stated time, the sample should be taken 15 minutes before the next sample (which can be delayed by 15 minutes if needed) so that every patient has a total of six samples.

7.5 Collection and storage of biological samples.

Each PK sample requires 2 mL of blood to be taken in collection tubes without anticoagulant and with uncoated interior (BD Vacutainer™ EST™ Blood Collection Tubes). Blood will be taken from a cannula to avoid multiple venepuncture. The total volume of blood taken (16 ml) should have no clinical impact on the patient. The blood samples will then be centrifuged for 10 min at 1500g. The serum

will be transferred to a storage tube that will be labelled with the participant's identification number, date and time of sampling and will be frozen at -80°C .

The serum will be kept frozen at -80°C at the participating hospitals. Once all PK samples for all patients at a site have been collected, they will be sent frozen to [name] laboratory at UFR Sciences de la Santé Simone Veil, University Versailles Saint Quentin ([name]) for PK analysis. No patient identifiable data will be transferred to the laboratory.

Once all analysis for this trial has been completed, all blood samples will be destroyed.

7.6 Follow-up assessments

The following parameters will be recorded during the follow-up time of 7 days or until discharge whichever is earlier:

- **Reaction at site of injection:** Each injection site will be inspected for local reactions at the same time as PK blood sampling and daily thereafter (for 7 days or until prior discharge).
- **Vital signs:** Participants will have their blood pressure, temperature, heart rate and respiratory rate recorded at the time of PK blood sampling.
- **Treatments:** Data on treatments likely to influence PK levels of TXA (blood product transfusion and IV fluids administration) will be collected from time of IM administration up to the time of the last PK sample.
- **Adverse events** as described in Section 9 will be recorded up to 7 days.

7.7 End of trial for participants

The trial ends at death, discharge or at 7 days, whichever occurs first.

7.8 Expected length of participation

Duration of participation for each participant	Treatment period: single dose of TXA (1 gram by 2 IM injections) Follow up: death, discharge or 7 days (whichever is earlier)
---	--

7.9 Summary of trial procedures

Procedure	Pre-hospital	Arrival at ED	IM TXA	Blood sampling period	Follow-up (Day 7, death or discharge whichever comes first)
Clinical administration of IV TXA	X	X (if not received before)			
Eligibility assessment		X			
Consent		X			X
Baseline data collection (from clinical records) Demographics and anthropometric data Vital signs (blood pressure, temperature, heart rate, respiratory rate) Renal function (creatinine) Parameters to assess severity of shock (base excess, blood lactate) Concomitant treatments including blood product transfusion		X			
IM TXA administration (1 gram/10 mL)			X		
Pharmacokinetic blood samples 2 baseline blood samples before the IM injection and 6 post IM blood samples				X	
Reaction at injection sites assessment				X	X
Vital signs: 
 Blood pressure Temperature Respiratory rate Heart rate 				X	X
Concomitant treatments (blood products and IV fluids)				X	
Adverse Events			X	X	X

7.10 Distinction between standard care and research

The only departure from standard care is the second TXA dose is given by IM injection with extra blood sampling. We will obtain data from the medical records (demographic, anthropometric, vital signs, blood test results, receipt of IV fluids and blood products, and adverse events). We will regularly inspect the injection site.

7.11 TXA quantitation

7.11.1 Efficacy

Due to its high specificity, mass spectrometry is recognized as the reference method for drug analysis. [name] team at Université Versailles Saint Quentin, France is experienced in mass spectrometry and has a record of publication in the development of methods to assess serum levels of TXA.²⁹⁻³⁴ TXA will be measured in serum samples with liquid chromatography coupled to mass spectrometry according to an analytical method validated following the EMA guideline on bioanalytical method validation.^{29,30}

7.11.2 TXA quantitation from serum samples

Serum samples shipped from the UK hospitals to the Université Versailles Saint Quentin (France) will be prepared for chromatography following the procedure detailed in Fabresse et al.³⁶ TXA will be measured in samples as previously described.³⁶ The advantages of this method over the others is the removal of phospholipids from plasma samples, high-sensitivity, wide dynamic range and validation according to the EMA guideline on bioanalytical method validation (EMA/CHMP/EWP/192217/2009Rev.1 Corr.2). The precision was in the range 1.2-3.0%, and accuracy between 88.4 and 96.6%.

Chromatography will be performed with an UltiMate 3000 Quaternary Rapid Separation Pump (Thermo Scientific Dionex, Les Ulis, France). A 2.6 µm Accucore Urea HILIC column (150 × 3 mm i.d.) (ThermoFisher) maintained at 50°C in an UltiMate 3000 Rapid Separation Thermostated Column Compartment (Thermo Scientific Dionex) will be used. Compounds will be ionized with a heated electrospray ionization source and detected with a triple quadrupole Quantiva mass spectrometer (ThermoFisher) using multiple reaction monitoring (MRM) in the positive ionization mode. Nitrogen (N2-45 nitrogen generator, VWR International, Fontenay sous bois, France) will be employed as sheath and auxiliary gas and argon (Messer, Puteaux, France) as a collision gas. A typical analytical series consists of 8 calibration standards, 24 samples, 6 quality controls and 10 rinses. For late sampling times where low concentrations can be expected, it may be necessary to adapt the method and add a vacuum evaporation step to concentrate the samples.

7.12 Premature exit of trial participant

Participants may exit the study at any time and for any reason. A previously given consent can be withdrawn. The investigator can withdraw a participant from the trial for any safety reason or if it is in the participant's best interest.

If a participant exits the trial prematurely or withdraws consent or refuses consent for continuation, data collected up to time of premature exit will be used.

7.12.1 Monitoring participants after the premature termination of treatment

In case of an adverse event, the investigator will complete an adverse event report and monitor the participants until the end of her/his participation in the research. If treatment is stopped prematurely due to a serious adverse event, a serious adverse event report will be completed. The serious adverse event will be monitored until the participant recovers or a steady state is reached.

7.12.2 Procedure for replacing participants

If consent procedures are complete but the IM dose is not given, the participant will be replaced. If the IM dose is given but no more than two post IM blood samples are taken, the participant will be replaced.

7.12.3 Full or partial discontinuation of the study

LSHTM (the Sponsor) may prematurely discontinue all or part of the trial, temporarily or permanently, in the following situations:

- If new information about the trial drug, in light of which the objectives of the study are unlikely to be achieved.
- LSHTM reserves the right to permanently suspend enrolment at any time if the enrolment targets have not been met.

If the trial is discontinued prematurely, the LSHTM Clinical Trials Unit (CTU) will inform the relevant REC and the MHRA of its decision within 15 days, together with justification for the decision.

8 TRIAL TREATMENT

8.1 Description and regulatory status of investigational medicinal product(s)

Tranexamic acid formulated for injection used in this trial is UK-licensed and commercially authorised and available on the UK market from several brands/manufacturers at the same concentration.³⁵

8.2 Preparation and labelling of Investigational Medicinal Product

TXA is commercially available in the UK and is labelled for IV use. The Sponsor will use an accredited supplier to relabel the ampoules in line with Annex 13 requirements for an open label clinical trial. Sites will choose the most appropriate needle size for IM administration from their clinical stock (between 19 - 25 Gauge and from 1 ½ inches up to 3" for large adults).

Labeling: Each ampoule will be labelled in accordance with Annex 13 requirements for an open label clinical trial.

Accountability: The Investigational Medicinal Product (IMP) will be sent to the named Clinical Trials Pharmacist at each site. The participating site pharmacy should have overview of the drug accountability. Records of all IMP shipments and administration to a patient must be kept on the drug accountability log. If the IMP stock received from the Sponsor is unexpected, wrong or damaged, the stock should be quarantined and LSHTM CTU contacted for further actions.

Storage conditions: Treatment packs should be stored at ambient temperature at the participating sites. No special temperature monitoring is required. In advance of the trial start, the clinical trials pharmacist/delegate will carry out a risk assessment of suitable storage in the emergency department to ensure the trial drug is available for use without delay.

8.3 Dosage schedules

Each patient will receive one dose of 1 gram of TXA divided in two IM injections (2 vials x 5 mL). Each 5mL will be injected separately in the thigh (rectus femoris or vastus lateralis), gluteal or deltoid muscles. The site of each injection will be recorded in the CRF.

8.4 Known drug reactions and interaction with other therapies

TXA solution for injection should not be added to blood for transfusion, or to injections containing penicillin.

8.5 Trial restrictions and the use of concomitant medication

Patients should receive all clinically indicated treatments. There is no restriction on the use of concomitant medication. In the event non trial TXA is given during the time of the PK sampling, the dose, route of administration, date and time should be recorded on the CRF.

8.6 Assessment of compliance with treatment

Two IM injections of TXA will be administered by investigators at each site who will record the date, time and body location of each TXA injection. If one or none of the injections is administered, the reason for this will be recorded in the CRF. The following will not be considered non-compliance with

the protocol: where a patient dies before receipt of the IMP or where a clinical reason is given for non-administration of the IMP.

9 PHARMACOVIGILANCE

All patients included in this trial will have a life threatening injury. It is expected that approximately 20% of patients will die from their injury. Events which occur as a consequence of the injury and represents progression of the injury (e.g. anaemia from blood loss, medical or surgical intervention for the injury), or events which commonly occur in this population independent of exposure to TXA IM administration, and those which are study endpoints does not need to be reported as an adverse event. All other events fulfilling the criteria below should be reported. If a patient develops an adverse event, the patient should be treated in line with local procedures.

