3.3 Secondary endpoints

- Local reactions at injection sites

- Adverse events

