9.1 Definitions

Term	Definition
Adverse Event (AE)	Any untoward medical occurrence in a participant to whom a medicinal product has been administered, including occurrences which are not necessarily caused by or related to that product. An AE can therefore be any unfavourable and unintended sign (including an abnormal laboratory finding), symptom, or disease having been absent at baseline, or if present at baseline, appears to worsen AND is temporally associated with medical treatment or procedure.
Adverse Reaction (AR)	
An untoward and unintended response in a participant to an investigational medicinal product which is related to any dose administered to that participant.
 
The phrase "response to an investigational medicinal product" means that a causal relationship between a trial medication and an AE is at least a reasonable possibility, i.e. the relationship cannot be ruled out.
 
All cases judged by either the reporting medically qualified professional or the Sponsor as having a reasonable suspected causal relationship to the trial medication qualify as adverse reactions. It is important to note that this is entirely separate to the known side effects listed in the Summary of Product Characteristics (SmPC). It is specifically a temporal relationship between taking the drug, the half-life, and the time of the event or any valid alternative aetiology that would explain the event.

Serious Adverse Event (SAE)	
A serious adverse event is any untoward medical occurrence that:
 
 • results in death • is life-threatening • requires inpatient hospitalisation or prolongation of existing hospitalisation • results in persistent or significant disability/incapacity • consists of a congenital anomaly or birth defect

	Other 'important medical events' may also be considered serious if they jeopardise the participant or require an intervention to prevent one of the above consequences. NOTE: The term "life-threatening" in the definition of "serious" refers to an event in which the participant was at risk of death at the time of the event; it does not refer to an event which hypothetically might have caused death if it were more severe.
Serious Adverse Reaction (SAR)	An adverse event that is both serious and, in the opinion of the reporting Investigator, believed with reasonable probability to be due to one of the trial treatments, based on the information provided.

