9.2 The role of the site investigator

The investigator must assess the seriousness criteria of each adverse event and record all serious and non-serious adverse events in the CRF.

The investigator must document serious adverse events as thoroughly as possible and provide a definitive medical diagnosis, if possible. Additionally, the causal relationship between the serious adverse events and the IMP is needed.

When completing the Adverse Event reporting form, the investigator will assign a causality using the definitions in the table below.

Relationship	Description
Suspected to be related	There is evidence to suggest a causal relationship with administration of the trial treatment and the influence of other factors is unlikely.
Not suspected to be related	There is little or no evidence to suggest there is a causal relationship (e.g. the event did not occur within a reasonable time after administration of the trial treatment). There is another reasonable explanation for the event (e.g. the participant's clinical condition, other concomitant treatment).

If there is any doubt about the causality, the site Principal Investigator (PI) or medical delegate will inform the LSHTM CTU. In the case of discrepant views on causality between the investigator and

others, all parties will discuss the case. In the event that no agreement is made, both points of view are to be recorded and reported onwards as required.

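### Section 9 exempts study endpoints and an unlisted class of common events from adverse-event reporting, although adverse events are a secondary endpoint and section 9.2 requires all of them to be recorded

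*Protocol*

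**What the plan says.** Section 9 of the protocol opens by exempting three classes of event from adverse-event reporting. One is the consequences or progression of the injury. Another is the trial's own endpoints: "those which are study endpoints does not need to be reported as an adverse event". For the remaining class, the protocol gives no list, frequency threshold or adjudicator, only this description: "events which commonly occur in this population independent of exposure to TXA IM administration". All events outside these classes are then made reportable under the criteria that follow.

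Section 3.3 names two secondary endpoints: "Local reactions at injection sites" and "Adverse events". Section 9.2 tells the investigator to "record all serious and non-serious adverse events in the CRF". Section 9.2.1 requires notification to the trials unit within 24 hours of any event assessed as serious.

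On causality, section 9.1 counts an adverse reaction when the link "is at least a reasonable possibility, i.e. the relationship cannot be ruled out". The investigator's form in section 9.2 reserves the related category for cases where "There is evidence to suggest a causal relationship with administration of the trial treatment and the influence of other factors is unlikely", and places events with another reasonable explanation, such as the patient's condition, in the unrelated category. The SAR definition in section 9.1 uses a third test, worded as probability and in the reporting investigator's opinion. Section 9.3.1 uses a fourth: suspicion by the investigator, the Sponsor or both.

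**The concern.** The endpoint exemption is circular. Adverse events are themselves a study endpoint, so the clause read literally exempts the thing that section 3.3 sets out to measure. It also exempts local reactions, although section 2.5 says that the foreseeable risks come from the intramuscular route.

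The exemption for common events asks the site to judge that an event is independent of the trial dose before anything is reported, so causality is decided at the point of capture. Section 9.2 points the other way. The two hospitals could follow the same protocol and collect different events.

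At stake are the completeness of a stated endpoint and the Sponsor's sight of serious events. Under section 9.3.1 the Sponsor assesses reported events only, and an event never recorded cannot be recovered at analysis. The protocol concedes in section 9.4 that intramuscular data are limited, and there is no data monitoring committee.

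**Working it through.** **Following four kinds of event through the text**

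| Event | Section 9 read literally | Other sections | Outcome |
|---|---|---|---|
| Non-serious local reaction | Exempt (endpoint) | 7.6 inspects each site at every PK sample, then daily to day 7 or discharge; 10.3.3 tabulates skin reactions | Counted |
| Local reaction meeting a seriousness criterion | Exempt (endpoint) | 7.6 has no seriousness assessment or notification step; 9.2.1 would require notification | Counted as a local reaction; route to the Sponsor contradictory |
| Other event that the site judges common and independent of the dose | Exempt | 9.2 would require recording and, if serious, 9.2.1 notification | Contradictory; may be missing from the adverse-event table and from Sponsor review |
| SAE reported, but ticked unrelated by the investigator | Not exempt | 9.2.1 notifies on seriousness alone; 9.3.1 lets the Sponsor's suspicion suffice | Reaches the Sponsor |

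The loss therefore arises where section 9 keeps an event from being reported.

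**Illustrating the size.** The protocol states no adverse-event rate or detection probability, so there is no figure to reproduce. Inputs:
- n = 30, from the Trial Summary. Dosed patients who are later replaced could make the safety population slightly larger.
- p, the true risk of an event per patient: assumed 5% or 10%.
- f, the share of events exempted at site: assumed 0% to 75%.

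Chance of recording at least one event = 1 − (1 − p(1 − f))^30.

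| f | p = 5% | p = 10% |
|---|---|---|
| 0% | 1 − 0.95^30 = 78.5% | 1 − 0.90^30 = 95.8% |
| 25% | 1 − 0.9625^30 = 68.2% | 1 − 0.925^30 = 90.4% |
| 50% | 1 − 0.975^30 = 53.2% | 1 − 0.95^30 = 78.5% |
| 75% | 1 − 0.9875^30 = 31.4% | 1 − 0.975^30 = 53.2% |

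**Exemption against causality form.** Let s_inv and s_spon be the chances that the investigator and the Sponsor suspect a true reaction, taken as independent. Share captured = (1 − f) × [1 − (1 − s_inv)(1 − s_spon)].

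- With f = 0 and s_inv assumed 50%: no Sponsor review gives 50%; s_spon = 50% gives 1 − 0.5 × 0.5 = 75%; s_spon = 80% gives 1 − 0.5 × 0.2 = 90%; s_spon = 100% gives 100%.
- With f = 25% or 50%, capture cannot exceed 75% or 50%, even with perfect Sponsor review.

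Sponsor review can largely make good the strict form for reported events. It cannot make good the exemption.

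**The case against.** The strongest reply is that other parts of the protocol prevent most of the harm, and much of that reply stands.

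- **Local reactions.** A reader might infer that this endpoint would be under-counted. The documents do not support that: sections 7.6, 7.9 and 9.6 schedule the inspections and section 10.3.3 tabulates the findings. What remains is that inspection alone gives a serious local reaction no expedited route.
- **Causality form.** A reader might infer that its stricter wording stops events from reaching the Sponsor within 24 hours, or blocks SUSARs. It does not. Notification depends on seriousness, doubtful cases go to the trials unit under section 9.2, and section 9.3.1 has the Sponsor assess causality itself. The section 9.1 definition also has assessors weigh alternative causes, which narrows the gap with the form. The thresholds still differ.
- **Scope of the exemption.** The clause on common events is limited to those independent of the intramuscular dose, and the document as a whole plainly expects adverse events to be recorded and coded. No site would read section 9 as abolishing reporting. But the qualifier is a causality judgement made before capture, and nothing says which event types fall inside it.
- **Documents not shown.** The safety reporting flow chart, CRF and SAE form (Appendices 11, 12 and 12A) may settle what is collected in practice. That limits what can be said about the operational effect; it does not remove the contradiction in the protocol text.

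**Conclusion.** The concern holds as an internal contradiction that should be fixed. Section 9 conflicts with sections 3.3, 9.2 and 9.2.1. Under its literal reading the adverse-event endpoint could be incomplete, and a serious local reaction or an exempted serious event might not reach the Sponsor. Under section 9.2 those events would be captured, so under-counting is a risk and not a certainty. Exempting injury progression is not in itself an error. The inconsistent causality wording is a lesser, separate fault.

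The size cannot be derived from the documents. The illustrative figures rest on assumed risks, exempted shares and sensitivities; what they show is that the exemption, not the form, sets the ceiling on capture.

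Three further readings go too far. Section 9 is not the trial's only safety filter: sections 9.3 to 9.3.3 provide continuous Sponsor assessment, risk/benefit reassessment and an annual report, and section 12.3 provides monitoring with source access. Nor does the plan guarantee a clean adverse-event table; its remark that there were no adverse effects describes the healthy-volunteer studies. Finally, two figures that a reader might compute do not measure this defect. The two-sided 95% upper limit for zero events in 30, 1 − 0.025^(1/30) = 11.6%, applies to any group of 30 with complete capture, and 20% × 30 = 6 expected deaths says nothing about how many events would be exempted.

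The primary endpoint, serum TXA concentration, is unaffected.

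**What to change.** Reconcile sections 3.3, 9, 9.1, 9.2, 9.2.1 and 9.3.1:

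1. Delete the exemption for study endpoints from section 9.
2. Replace the clause on common events with a closed list of event types that are exempt from expedited reporting only, and state that they are still recorded on the CRF.
3. State that a local reaction meeting any seriousness criterion is reported as an SAE, in addition to being recorded at the scheduled inspection.
4. Use the section 9.1 adverse-reaction threshold, a reasonable possibility, in the SAR definition, the investigator's causality table and the Sponsor's assessment, and say in each place that suspicion by either party is enough.

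Check the CRF, the SAE form and the safety flow chart against the amended text. The cost is a wording amendment, matching wording on the SAE form, and a few more event forms across 30 patients. The sample size, the sampling schedule and the pharmacokinetic analysis do not change.
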